Following completion of tPA infusion or initiation of mechanical thrombectomy (arterial puncture), whichever occurs sooner, eligible adult subjects will receive 3K3A-APC or placebo 30 to 120 minutes later given as a 15-minute infusion. Subjects will receive another 15-minute infusion of 3K3A-APC every 12 hours (+/- 1 hour) for up to 5 total infusions. Four dose levels will be considered for this study: 120, 240, 360, and 540 µg/kg. For the purposes of this study, we assume an established background symptomatic intracerebral hemorrhage (SICH) rate of 3-6%²⁻⁷. Correspondingly, the MTD will be defined as the highest dose with a DLT rate of 10% or less. Subjects will be enrolled to 3K3A-APC dose cohorts in groups of four (three to specified treatment

dose and one to placebo). Subjects will generally be enrolled at the dose estimated from the assumed dose-response model and prior data to be closest to the MTD. However, the initial cohort will start at the lowest dose level ($120 \mu g/kg$) and the dose level may be escalated by no more than one dose between consecutive cohorts (there are no restrictions on dose level de-escalation). Intra-subject dose modification is not permitted during the study.

Prior to starting the CRM, based on a best estimate from the literature and previous studies, the four dose levels will be assigned prior probabilities as indicated in Table 3 below.

Table 3. Assumed prior probabilities of toxicity at four dose levels considered for the study:

Dose Level	120	240	360	540
Prior Probability of Toxicity	5%	7%	9%	11%

When designing a CRM, O'Quigley, Pepe and Fisher recommend using a single-parameter doseresponse model $\psi(x_i^*, a)$, which is probability of toxicity at dose x_i^* for some unknown parameter, a, which defines the shape of the dose-toxicity function. For this study, a hyperbolic tangent doseresponse model will be used, in which

$$\psi(x_i^*,a) = \left\{\frac{\tanh(x_i^*+1)}{2}\right\}^a.$$

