Four dose levels will be considered for this study: 120, 240, 360, and 540 µg/kg. Following completion of tPA infusion, or initiation of mechanical thrombectomy (arterial puncture), whichever is sooner, eligible adult subjects will receive 3K3A-APC or placebo 30 to 120 minutes later given as a 15 minute infusion. Subjects will receive another 15 minute infusion of study treatment every 12 hours (+/- 1 hour) for up to 5 total doses (or until discharge, whichever occurs first). It is preferable not to skip doses of study drug, and should a dose need to occur outside of the +/- 1 hour window (which will be reported as a protocol deviation), doses should never be given within 8 hours of one another.

For the purposes of this study, we assume an established background symptomatic intracerebral hemorrhage (SICH) rate of 3-6% (Wahlgreen et al, 2007; Hacke et al, 2008; Berkhemer et al, 2015; Campbell et al, 2015; Goyal et al, 2015; Saver et al, 2015). Correspondingly, this study aims to identify the highest dose with a DLT rate of 10% or less. Subjects will be enrolled to 3K3A-APC dose cohorts in groups of four (three to specified treatment dose and one to placebo). Subjects will generally be enrolled at the dose estimated from the model at that time, based on the assumed original dose-response model and all prior observed data to date, as the highest dose with a DLT rate of 10% or less. However, the initial cohort will start at the lowest dose (120 µg/kg) and the dose level may be escalated by no more than one dose between consecutive cohorts (there are no restrictions on dose level de-escalation). Intra-subject dose modification is not permitted during the study. After the final group of subjects is enrolled, the final MTD will be defined as the highest dose with an estimated toxicity probability less than or equal to the target toxicity level of 10%.

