After each evaluable subject in a cohort is adjudicated by the SRC as having or not having a DLT, the CRM will be updated by an unblinded study statistician and independently verified by a second unblinded study statistician. Specifically, the posterior mean of a will be re-estimated using the prior probabilities from Table 1 and all evaluable data for each cohort of subjects. Subsequently, the posterior probabilities of observing a DLT at each 3K3A-APC dose, $(x_{120}, x_{240}, x_{360}, x_{540})$, can be calculated by solving the above equation for:

$$\psi(x_i^*, \hat{a}), i = 120, 240, 360, 540.$$

Based upon that estimate, the largest dose with estimated toxicity probability, $\psi(x_i^*, \hat{a})$, less than or equal to 10% will be allocated to the next cohort of randomized participants. If this dose is more than one level higher than the previous dose allocated, the dose will only be increased one level. Dose de-escalation is not subject to any restrictions. There are 22 cohorts of four subjects each planned, but fewer may be enrolled should the study meet any of the stopping criteria.

In summary, the CRM model will proceed as follows:

- Enroll the first 4 subjects into cohort 1.
 - Treat one of the four subjects (chosen randomly) with placebo.
 - Treat the other three subjects with the lowest dose: 120 µg/kg.
 - Observe the number of subjects (out of the three treated subjects) that have a DLT per the study DLT definition.
 - Determine the number of evaluable subjects in the cohort. Any given subject who receives only one dose of study drug and does not experience a DLT will not be considered “evaluable”, and will not be included in the CRM calculation (i.e., for subjects with no DLT observed, two or more doses will need to be administered to be included).
 - Based upon the observed information from the evaluable subjects in the cohort, refit the assumed dose-response curve.
- Initially (through version 7.1 of the protocol), the re-estimated dose-response curve using all cohorts enrolled to date was then used to determine the highest dose level of the four under consideration that has an estimated probability of toxicity less than or equal to 10%.
 - The next cohort of subjects is treated at the dose level specified above – unless the chosen dose level is more than one level higher than the current level. If so, treat the next cohort of subjects at the next dose level above the current level.

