- Based on a DSMB recommendation, this process was changed as of version 8.0 of the protocol. The basic process proceeds as described above, but once all subjects in a given cohort (n) have been enrolled, data from all prior cohorts (cohort 1, cohort 2, ..., cohort $n-1$) are used to determine the dose level of cohort $n+1$.
 - If enrollment is rapid such that both cohort ($n-1$) and cohort (n) are filled and awaiting DLT review, new subjects enrolled will be randomized to placebo until cohort ($n-1$) has been reviewed. (For example, if both cohort 13 and 14 are filled and awaiting review, subjects will be randomized to placebo until cohort 13 is closed and the model is rerun to determine the dose for cohort 15).
- Repeat the process.

At the conclusion of the study, the MTD will be selected using the rules specified above for the implementation of the CRM model. Specifically, the model will be run a final time using all observed data and the MTD will be defined as the highest dose with an estimated DLT rate of 10% or less based on that final model. The study will stop once the first of the following criteria have been met:

- The maximum number of cohorts (22) has been observed.

- If at any time after half of the cohorts (11) have been observed, two consecutive iterations suggest a 15% or higher toxicity rate at the lowest dose (stop for safety).
- If the study proceeds straight to the highest dose, and then observes 9 successive cohorts at the highest dose with no observed toxicity (stop and declare the highest dose the MTD).
 - Through simulation, it was determined that it would extremely unlikely to observe no DLTs after 9 successive cohorts if the true toxicity rate were 10%. Thus, after 9 cohorts we would have sufficiently determined that all doses under consideration are safe and early stopping would be justified.

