9. SAMPLE SIZE CONSIDERATIONS

9.1 Primary Outcome

In order to assess the adequacy of the sample size, we conducted a simulation study to examine the ability of the study to identify the MTD under a range of assumed scenarios. The scenarios under consideration are summarized below in Table 4.

Table 4. Assumed True Toxicity Probabilities for Simulation Scenarios

Scenario	Description	Dose Level ($\mu\text{g}/\text{kg}$)			
		1 (120)	2 (240)	3 (360)	4 (540)
1	MTD = Dose 4	0.05	0.05	0.05	0.05
2	MTD = Dose 4	0.05	0.05	0.07	0.10
3	MTD = Dose 3	0.05	0.07	0.10	0.15
4	MTD = Dose 2	0.05	0.10	0.15	0.20
5	MTD = Dose 1	0.10	0.15	0.20	0.25
6	No MTD	0.15	0.20	0.25	0.30

The scenarios describe the full range of possibilities:

- Scenario 1 considers the case where all doses are safe (i.e., true toxicity probability is below the target threshold for each dose).

- Scenarios 2-5 consider the case where the true target toxicity level of 10% occurs at each successive dose level under consideration.
- Scenario 6 considers the case where no dose level is safe (i.e., true toxicity probability is above the target threshold for all doses).

The results of the simulation study are summarized in Table 5, and contrasted to the results from a pure 3+3 design (which was proposed in the original version of the protocol). Below, we provide a short summary of the findings from the simulation study:

- In scenario 1, both CRM approaches and the 3+3 method select the highest dose with high probability.
- In scenarios 2-5, both CRM approaches generally does a better job at selecting the “correct” dose as the MTD. The 3+3 method does slightly better at selecting the highest dose when it is the MTD (scenario 2). However, this comes at a cost of “overshooting” the MTD when the true MTD occurs at a lower dose – as high as 88% under scenario 5.
- In scenario 6, the CRM approaches correctly conclude that no dose satisfies the criteria of an MTD over half of the time, whereas the 3+3 has a small probability of declaring no MTD and seems to select any of the four doses in a near uniform manner.

Table 5. Results of Simulation Study

Scenario	Dose Level	% Recommended			# Subjects Allocated			% True Toxicity CRM
		CRM	CRM _{lag}	3+3	CRM	CRM _{lag}	3+3	
1	None	0%	1%	1%				
	120	2%	2%	2%	8.1	11.5	3.5	5%
	240	3%	4%	2%	5.3	8.9	3.4	5%
	360	4%	5%	3%	5.4	8.0	3.6	5%
	540	91%	88%	91%	42.2	32.6	45.2	5%
2	None	1%	1%	1%				
	120	4%	4%	2%	9.3	12.4	3.4	5%
	240	9%	9%	2%	8.3	10.8	3.4	5%

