	360	19%	19%	10%	10.4	11.4	4.4	7%
	540	68%	67%	86%	36.8	29.7	33.8	10%
3	None	1%	1%	1%				
	120	10%	10%	2%	13.8	15.7	3.5	5%
	240	25%	25%	4%	14.0	14.9	3.6	7%
	360	32%	31%	19%	14.2	13.9	5.0	10%
	540	32%	33%	74%	23.6	20.9	23.1	15%
4	None	1%	2%	1%				
	120	27%	26%	2%	22.0	22.5	3.5	5%
	240	42%	42%	8%	19.1	19.3	4.1	10%
	360	21%	21%	29%	12.4	12.6	5.6	15%
	540	9%	10%	59%	12.1	11.1	15.5	20%
5	None	21%	20%	3%				
	120	54%	54%	9%	37.4	36.9	4.0	10%
	240	20%	20%	16%	12.5	13.9	4.4	15%
	360	5%	5%	32%	6.1	6.4	5.2	20%
	540	1%	1%	41%	4.8	3.8	9.4	25%
6	None	61%	61%	6%				
	120	34%	34%	19%	39.4	39.0	4.5	15%
	240	4%	4%	22%	6.2	7.7	4.5	20%
	360	1%	1%	29%	2.8	2.7	4.4	25%
	540	0%	0%	24%	1.9	1.3	5.2	30%

In summary, both the modified CRM and lagged CRM approaches generally have better performance than the 3+3 design with respect to successfully recommending the correct dose as the MTD (based on prior assumptions), and either would be well suited to achieve the goals of this study. The modified CRM design

being used here performs better than the more traditional approach at identifying the true MTD when it occurs at one of the intermediate doses. Clearly, better accuracy could be achieved by increasing the sample size for the study. However, when weighted against the costs of a larger study, the proposed sample size provides the right balance with respect to selecting the correct dose across all scenarios, and considering the probabilities of both “undershooting” and “overshooting” the assumed true MTD. Some efficiency is sacrificed by using the lagged version of the modified CRM. However, this minor loss of efficiency is completely offset by the operational advantages of requiring fewer “extra placebo subjects” to be enrolled.

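### The CRM operating characteristics in Table 5 do not come from the dose-selection rule the plan states; they match a different rule (dose with estimate closest to 10%)

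*SAP*

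**What the plan says.** SAP section 7 allocates the largest dose whose estimated toxicity is "less than or equal to 10% will be allocated to the next cohort of randomized participants". At the end, "the MTD will be defined as the highest dose with an estimated DLT rate of 10% or less based on that final model". SAP section 1 and the algorithm in Protocol 8.1.1 say the same. The Protocol synopsis and 8.1.1 also carry looser wording: "Subjects will generally be enrolled at the dose estimated from the assumed dose-response model and prior data to be closest to the MTD". Both documents define the MTD itself by the 10% ceiling, and neither tells the statistician to pick the dose whose estimate lies nearest to 10%.

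The other design elements are explicit:
- a skeleton of 5, 7, 9 and 11%
- three treated subjects per cohort and at most 22 cohorts
- "the dose level may be escalated by no more than one dose between consecutive cohorts"
- a safety stop, after 11 cohorts, when two consecutive fits put the lowest dose at 15% or more
- a stop if the trial goes straight to the top dose and then "observes 9 successive cohorts at the highest dose with no observed toxicity"

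Table 5 is presented as this design's performance; SAP 9.1 introduces it with "we conducted a simulation study to examine the ability of the study to identify the MTD under a range of assumed scenarios". The text concludes that "the proposed sample size provides the right balance with respect to selecting the correct dose across all scenarios", and explains the *None* row thus: "In scenario 6, the CRM approaches correctly conclude that no dose satisfies the criteria of an MTD over half of the time". The prior distribution for the model parameter a and the number of simulated trials are not given.

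**The concern.** Table 5 is the only quantitative support for the sample size of the primary objective. If it describes another rule, its success, undershoot and overshoot percentages are not those of the trial as written.

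The two rules can also assign different doses to the same data. With estimates of 8% at one level and 11% at the next, the ceiling rule picks the lower dose and the nearest-to-target rule the higher. SAP section 7 has two statisticians run a SAS program for each cohort, but neither document shows which rule that program contains. A double run would not expose an error common to both.

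**Working it through.** **Model.** In either document's tanh form, solving for the dose label so that the prior toxicity is p_i gives ψ_i = p_i^a, with p = 0.05, 0.07, 0.09, 0.11. The estimate is p_i raised to the posterior mean of a. True rates are those of Table 4.

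**Assumptions where the documents are silent.** Unit-exponential prior for a; all three treated subjects evaluable; a cohort with no admissible dose is treated at 120 so that the simulation can continue; safety stop first able to act at fit 12 (acting from fit 11 changes results by about 1 point). Each scenario has 10,000 trials, so the standard error is at most √(0.5×0.5/10,000) = 0.5 point.

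**Reproducing Table 5, unlagged CRM.** Only the selection rule differs between the last two columns. Where two values appear, the first reads *None* as no dose at or below 10%, the second as a safety stop only.

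| Quantity | Table 5 | Stated rule (≤10%) | Closest to 10% |
|---|---|---|---|
| Sc. 1 correct | 91% | 86% | 90.8% |
| Sc. 2 correct | 68% | 59% | 67.4% |
| Sc. 3 correct | 32% | 27% | 31.0% |
| Sc. 4 correct | 42% | 37.5% | 41.7% |
| Sc. 5 correct | 54% | 30% or 64% | 54.4% |
| Sc. 5 *None* | 21% | 54% or 20% | 20.5% |
| Sc. 6 *None* | 61% | 90% or 61% | 60.5% |
| Sc. 4 subjects at 120 | 22.0 | 27.8 | 22.0 |

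The closest rule, with *None* meaning a safety stop, matches all 30 selection percentages to within about 2 points and all 24 allocations to within 0.6 subjects. The scenario 1 to 4 figures and the allocations do not depend on how *None* is read.

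**Undershoot and overshoot.**
- Scenario 3, Table 5: 10+25 = 35% below the MTD and 32% above. Stated rule: 45–48% and 24%.
- Scenario 4, Table 5: 27% below and 21+9 = 30% above. Stated rule: 33–40% and 21%.

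**Sensitivity to the prior.** Five priors were run under the stated rule: unit exponential; gamma with shape 2 and mean 1; lognormal with log-variance 1.34 and 0.5; uniform(0,3). Correct selection ranged over 85–91, 59–64, 25–27 and 37–40% in scenarios 1 to 4, and 30–33% or 64–66% in scenario 5. No prior tried took scenario 2 above 64% (Table 5: 68%). Only uniform(0,3) closes the scenario 1 gap, and under that prior even the closest rule misses Table 5 by up to 5 points.

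**Lagged column.** With the ≤10% rule, the consecutive-cohort cap and the lag applied throughout, correct selection is 84/59/26/36/30% (*None* as no dose at or below 10%) against 88/67/31/42/54%. Subjects at the four doses in scenario 1 are 13.5/6.1/6.2/36.5 against 11.5/8.9/8.0/32.6. A close fit (percentages within 1.7 points, allocations within 0.5 subjects) needs three departures from the text: the closest rule, the cap counted from cohort n−1, and a stop after 12 DLT-free cohorts at any dose.

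A prior-free check on the stop uses scenario 1, where every dose has a 5% rate. Table 5's totals are 8.1+5.3+5.4+42.2 = 61.0 unlagged and 11.5+8.9+8.0+32.6 = 61.0 lagged.
- Stop after 12 clean cohorts: 66 − 30×0.95^36 = 61.3.
- Nine cohorts at 540 under a lag need 13 cohorts with the consecutive cap: 66 − 27×0.95^39 = 62.3.
- They need 15 with the n−1 cap: 66 − 21×0.95^45 = 63.9.

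**The uncovered state.** After one DLT in three at 120, the posterior mean of a is 0.493 (unit exponential), so the estimate at 120 is 0.05^0.493 = 22.8%; over the five priors it is 15–23%. No dose is then admissible, and the safety stop cannot act for many cohorts. In scenario 1 the chance of at least one DLT in cohort 1 alone is 1 − 0.95^3 = 14.3%. Over the whole trial, 18–30% of scenario 1 trials reach this state, depending on the prior.

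**The case against.** The strongest objection is the undisclosed prior. The 5-to-9-point gaps are unit-exponential results; over the five priors they are about 0–6, 4–9, 5–7 and 2–5 points in scenarios 1 to 4. That qualification stands for the size. It does not rescue the table, because no prior tried under the ceiling rule reproduces it as a whole.

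Scenario 5 has no fixed direction, and under the safety-stop reading of *None* the scenario 5 and 6 *None* rows agree with Table 5. That also stands. But that reading departs from the SAP's own explanation of *None*, and it leaves errors of up to 13 points: scenario 4 at 120, 40% against 27%; scenario 3 at 120, 20% against 10%; scenario 5 at 120, 64% against 54%.

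The closest rule is an inference. An 11% ceiling with the same prior gives 90/68/30/40% in scenarios 1 to 4, though it fits scenario 5 (58%) and the allocations (up to 1.9 subjects off) less well. Either way, the simulated rule is not the written one. The Protocol's closest-to-the-MTD phrase is not a disclosure, since the MTD is itself defined by the 10% ceiling.

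The lag reconstruction is a fit to unseen code, and the trial applied the lag only from protocol version 8.0. The n−1 anchor and the 12-cohort stop are needed for the mean allocations, not for the selection percentages. The main conclusion does not rest on them.

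Finally, the CRM still does better than 3+3 in scenarios 3 and 4, and in scenario 5 on either reading of *None*. The written rule also overshoots less. Both points are accepted.

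**Conclusion.** The concern holds. Table 5 does not describe the rule in SAP section 7 and Protocol 8.1.1. With a unit-exponential prior, correct selection is overstated by about 5 points in scenarios 1, 3 and 4 and 9 in scenario 2; other priors move these gaps as shown but do not remove the mismatch. In scenario 5 the stated 54% should be about 30% or 64%. In scenario 6, Table 5 understates the correct conclusion (61% against 87–90% over the five priors) if *None* means what the SAP says it means.

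The written rule undershoots more and overshoots less than the sample-size argument claims. That the table came from a closest-to-10% rule is very well supported for the unlagged column; the three lagged departures are the simplest fit found. Only the code can confirm either. Because these figures are the stated basis for the primary-objective sample size, the table must be corrected.

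**What to change.** 1. Inspect the simulation code and the SAS dose-recommendation program for the selection rule, the meaning of *None*, the cohort from which the escalation cap is counted under the lag, and the no-toxicity stop.
2. Reconcile the rule text in both documents with them, including the closest-to-the-MTD sentence in the Protocol synopsis and 8.1.1. This review takes no position on which dose rule is right; the passages must agree with each other and with the code.
3. State what happens when no dose has an estimate at or below 10% before the safety stop can act.
4. State the prior for a and the number of simulated trials.
5. Re-run both CRM columns under the reconciled rule and replace Table 5 and its summary text in SAP 9.1 and Protocol 8.3.1.

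The cost is a few hours of simulation plus wording changes. Some figures will look less favourable and some more. No additional patients are needed.

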9.2 Secondary Outcome (Bleed Rates)

We also assessed the power of the study to evaluate bleed rates between all treated subjects (collapsed across doses) versus placebo subjects. Previous experience (Derex et al, 2004; Kidwell et al, 2004; Fiehler et al, 2007; Cheng et al, 2013; Harada et al, 2013; Kimura et al, 2013; Shoamanesh et al, 2013) suggests that the MRI-detected bleed rate for tPA-treated subjects should be approximately 30%-40%. Furthermore, it is expected from pre-clinical studies that treatment with APC could lead to a rather dramatic decrease in bleed rates for 3K3A-APC treated subjects (Cheng et al, 2006; Wang et al, 2012; Wang et al, 2013). Pre-clinical data suggest that 3K3A-APC could reduce bleeding seen after IV tPA or after mechanical thrombectomy (Wang et al, 2012; Wang et al, 2013). Thus, it is expected that the study could observe a difference between the groups as substantial as a reduction from a 40% bleed rate among placebo subjects to a lack of observed bleeding in the treated group. However, to assess power over a range of conditions, we computed power for all combinations of the following conditions:

- Placebo group bleed rates of 20%, 30%, and 40%
- 3K3A-APC treated group bleed rates of 0.5%, 5%, and 10%
- Overall sample sizes of 48 (36 treated / 12 control) and 88 (66 treated / 22 control) – in order to assess power under the scenario where the trial proceeds to the end and under the scenario where the study stops early for lack of observing any toxicity at the highest dose

Table 6 provides a summary of these power calculations. In general, we find:

- *If the original assumptions are correct:* We would have very high power (>90%) in either scenario.
- *If the original assumption regarding the placebo rate is correct, but the treated rate is a bit higher:* We would have very good power (>85%) if the study proceeds to the end. We would have lower, but a still acceptable level of power (>64%) if the study stops due to a lack of observed toxicity after 12 cohorts.
- *If the original assumption regarding the treatment rate is correct, but the placebo rate is a bit lower:* We would have decent power (>66%) in either scenario, or very good power (>84%) in the scenario where the study proceeds to the end.
- *If both assumptions are wrong (placebo rate lower, treatment rate higher):* There is lower power overall, but still reasonable power in a number of settings (such as 30% placebo rate versus 10% treated rate).

In conclusion, it appears that the study has adequate power to detect differences in bleeding of interest, even if our assumptions are slightly optimistic. We believe that this sufficiently supports the adequacy of the comparison of bleeding rates.

Table 6. Power for Comparing Bleed Rates

Assumed Bleed Rate in Treated Group	Assumed Bleed Rate in Placebo Group					
	20%		30%		40%	
	N = 48	N = 88	N = 48	N = 88	N = 48	N = 88
0.5%	66%	84%	82%	95%	92%	99%
5%	39%	56%	63%	83%	80%	96%
10%	18%	26%	41%	61%	64%	85%

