In conclusion, it appears that the study has adequate power to detect differences in bleeding of interest, even if our assumptions are slightly optimistic. We believe that this sufficiently supports the adequacy of the comparison of bleeding rates.

Assumed Bleed Rate	Assumed Bleed Rate in Placebo Group								
in Treated Group	20)%	30)%	40%				
	N = 48	N = 88	N = 48	N = 88	N = 48	N = 88			
0.5%	66%	84%	82%	95%	92%	99%			
5%	39%	56%	63%	83%	80%	96%			
10%	18%	26%	41%	61%	64%	85%			

Table 6. Power for Comparing Bleed Rates (Assumes Chi-Square Test, Significance Level = 0.05, and 75% of Subjects Assigned to Treatment)

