1. STUDY DESIGN

This is a multicenter, prospective, randomized, placebo-controlled, double-blinded Phase 2 study intended to evaluate the safety, pharmacokinetics (PK), and preliminary efficacy of 3K3A-APC following administration of tPA, mechanical thrombectomy, or both in subjects with moderate to severe acute ischemic stroke. The study will utilize the continual reassessment method (CRM, O’Quigley et al, 1990). The original version of the CRM method proposed enrolling one subject at a time. However, others have shown that the performance of the CRM may be improved by enrolling cohorts instead of a single subject (Goodman et al, 1995). Correspondingly, this study will utilize a modified version of the CRM in order to establish a maximum tolerated dose (MTD).

The study will randomize approximately 115 subjects, which includes a planned 88 subjects in 22 cohort groups of four (each cohort will include one placebo and three study drug treated subjects). Additional placebo subjects who will be enrolled during safety review pauses will also be included. While placebo is not needed to determine the MTD, a placebo group has been included to conduct secondary analyses to examine for a reduction of pre-clinical tPA / mechanical thrombectomy-related hemorrhage and to obtain preliminary efficacy data that may be useful for the planning of future studies. It is predicted from pre-clinical studies that treatment may reduce thrombolysis-related hemorrhage.

Subjects will not be considered part of the intent-to-treat (ITT) cohort until they receive any amount of 3K3A-APC or placebo. For example, ‘Early Responders’ – defined as subjects whose symptoms resolve between initial randomization and initiation of Investigational Medicinal Product (IMP) infusion such that they are no longer eligible (repeat NIHSS < 5) – will be removed from the study and replaced. A Safety Review Committee (SRC) will review the safety data for each potential dose limiting toxicity (DLT), and make a final determination as to whether or not an incident should be classified as a DLT. At any time if enrollment is so rapid that two consecutive cohorts are awaiting DLT review, the IWRS will randomize any enrolled patients to placebo so as to preserve site-level blinding and trial enrollment momentum. These extra placebo treated subjects will enhance the power to detect a change in bleed rates for 3K3A-APC-treated subjects.

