6.3. Secondary Bleed Rate (Hemorrhage & Microbleeds) Analysis

The secondary bleeding analysis will be based on the results of the Day 30 MRI scans. Correspondingly, the analysis population for this secondary analysis will include all subjects who had a Day 30 scan collected.

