8.2 Analysis of Hemorrhage Rates

The incidence of hemorrhage, overall and by type (as defined above), will be summarized in a table similar to the one below:

Table 3. Bleeding Rates

Type	Total (N = XX)	Treated (N = XX)	Placebo (N = XX)	P-Value
Hemorrhage (Volume > 0.06 mL)	XX (%)	XX (%)	XX (%)	X.XX
(Volume > 0 mL)	XX (%)	XX (%)	XX (%)	X.XX
(Volume > 0.5 mL)	XX (%)	XX (%)	XX (%)	X.XX
(Volume > 1.8 mL)	XX (%)	XX (%)	XX (%)	X.XX
Microbleeds	XX (%)	XX (%)	XX (%)	X.XX

To assess tPA/mechanical thrombectomy-related hemorrhage rates across the two groups, all treated subjects (regardless of dose) will be compared to placebo subjects using a Pearson chi-square test. This test will assess the null hypothesis that there is no relationship between treatment group assignment and hemorrhage rates versus the alternative hypothesis that the groups differ with respect to hemorrhage rates. If any of the expected cell counts are too small to justify the use of the Pearson chi-square test, Fisher’s Exact test will be used instead.

If we fail to reject H_0 , then we will conclude that there is no significant difference between the placebo and 3K3A-APC groups. If H_0 is rejected, then we will conclude that the two groups differ with respect to hemorrhage rates – with the direction of the difference indicating which group has an increased (decreased) risk of hemorrhage. For example, if H_0 is rejected and the hemorrhage rate is lower in the 3K3A-APC group, then we will conclude that participants in the 3K3A-APC group have a significantly lower rate of hemorrhage than participants in the placebo group.

An additional analysis will compare the total hemorrhage rates among placebo subjects and subjects treated at each dose level (assuming a sufficient number of subjects were treated at that level). Again, if the assumptions of the Pearson chi-square test are not met, then Fisher’s exact test will be used instead.

All prior analyses will be repeated to compare the groups with respect to incidence of microbleeds at Day 30.

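### SAP 9.2 states chi-square power for the bleed comparison; under the Fisher fallback in SAP 8.2 the early-stop case (36 treated, 12 placebo; 0.5% vs 20%) has about 44%, not above 66%

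*SAP*

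**What the plan says.** SAP 9.2 computes power for "Overall sample sizes of 48 (36 treated / 12 control) and 88 (66 treated / 22 control". The smaller size is a stop after 12 cohorts because no toxicity is seen at the highest dose. The grid crosses placebo rates of 20, 30 and 40% with treated rates of 0.5, 5 and 10%. Table 6 gives 66% (N = 48) and 84% (N = 88) for 0.5% vs 20%, and the text summarises this as "We would have decent power (>66%) in either scenario".

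The protocol's copy of the table says which test was powered: "Power for Comparing Bleed Rates (Assumes Chi-Square Test, Significance Level = 0.05". The SAP's caption, in the text available, reads only "Table 6. Power for Comparing Bleed Rates" and names no test.

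The planned analyses differ between the documents. Protocol 8.5.2 names only Pearson's chi-square test. SAP 8.2 also starts with Pearson but adds a condition: "If any of the expected cell counts are too small to justify the use of the Pearson chi-square test", Fisher's exact test is used instead. No number defines too small.

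Two other statements affect the group sizes. SAP 1 says of placebo subjects enrolled during review pauses: "These extra placebo treated subjects will enhance the power to detect a change in bleed rates". SAP 6.3 says "the analysis population for this secondary analysis will include all subjects who had a Day 30 scan collected".

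**The concern.** A power statement should describe the test that will be run. Here the SAP carries over the protocol's chi-square figures, adds a Fisher fallback, and does not redo the power for the combined rule. With 12 placebo subjects and a treated rate near zero, very few bleeds are expected, so the fallback is the usual route. Fisher is conservative in such sparse tables, so the loss could be large.

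SAP 9.2 uses these figures to conclude that power is adequate even if its assumptions are slightly optimistic. If the trial stopped early and the comparison were not significant, a reader relying on >66% could give that null result more weight than it deserves. The missing cutoff also leaves the choice of test open until the data are seen.

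**Working it through.** **Inputs.** Sizes 36/12 and 66/22 and the bleed rates: SAP 9.2. Level 0.05: SAP 6. Two-sided, because the alternative in SAP 8.2 is non-directional. Cutoffs of 0.51, 1 and 5 for the smallest expected count are my assumption, since the SAP gives none.

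**Step 1: reproduce the stated figure.** Pooled normal approximation to the chi-square test, 36/12, 0.5% vs 20%:
- Pooled rate = (36 × 0.005 + 12 × 0.20)/48 = 2.58/48 = 0.05375.
- SE under the null = √[0.05375 × 0.94625 × (1/36 + 1/12)] = 0.0752.
- SE under the alternative = √[0.005 × 0.995/36 + 0.20 × 0.80/12] = 0.1161.
- z = (0.195 − 1.96 × 0.0752)/0.1161 = 0.41, so power = 65.9%. Stated: 66%.

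The same formula gives 84.3% at 66/22 (stated 84%), and all 18 cells of Table 6 reproduce within one point.

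**Step 2: does the fallback apply?** The total expected number of bleeds is 2.58, so the smallest expected count is about 2.58 × 12/48 = 0.65. Enumerating all tables at 36/12, 0.5% vs 20%, the smallest expected count is below 1 with probability 75% and below 5 with probability of about 100%.

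**Step 3: the deciding outcome, 0/36 vs 2/12.**
- Smallest expected count = 2 × 12/48 = 0.50.
- Pearson: χ² = 48 × (36 × 2)²/(36 × 12 × 2 × 46) = 6.26, p = 0.012. Rejects.
- Fisher: C(12,2)/C(48,2) = 66/1128 = 0.0585. Does not reject. (The other two tables with these margins are more probable, so this is also the two-sided p.)
- Probability at 0.5% vs 20%: 0.995³⁶ × 66 × 0.2² × 0.8¹⁰ = 0.835 × 0.283 = 0.237.

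**Step 4: power under the SAP rule** (exact enumeration; Fisher if the smallest expected count is below the cutoff, otherwise Pearson without continuity correction). Treated rate 0.5%, 36/12:

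| Placebo rate | Table 6 | Exact Pearson | Probability of 0/36 vs 2/12 | SAP rule |
|---|---|---|---|---|
| 20% | 66% | 67.5% | 23.7% | 43.8% |
| 30% | 82% | 88.4% | 14.0% | 74.4% |
| 40% | 92% | 96.8% | 5.3% | 91% |

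That one outcome accounts for the drop in each row (67.5 − 23.7 = 43.8). Results at cutoffs 0.51, 1 and 5 agree to within 0.1 point. At 66/22, 0.5% vs 20%, the SAP rule gives 83.7 to 83.8%.

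**Step 5: extra placebo subjects.** 36 treated, 0.5% vs 20%:

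| Placebo subjects | Cutoff 1 | Cutoff 5 |
|---|---|---|
| 12 | 43.8% | 43.8% |
| 15 | 59.8% | 55.8% |
| 17 | 64.8% | 64.8% |
| 18 | 68.8% | 68.8% |
| 20 | 75.7% | 75.4% |
| 27 | 88.0% | 75.6% |

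Power is below 66% at every number from 12 to 17 and above it at every number from 18 to 27, at both cutoffs. The plan implies about 115 − 88 = 27 extras in all. If they accrued evenly (an assumption), about 27 × 12/22 = 14.7 would be in by cohort 12, giving roughly 36/27. In the other direction, if 10% of Day 30 scans were missing in each arm (also an assumption), 32/11 would give 38%.

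**Step 6: where the cutoff matters.** 10% vs 40%:
- 36/12: 65% at cutoff 1, 56% at cutoff 5 (text: >64%).
- 66/22: 86% at cutoff 1, 83% at cutoff 5 (text: >85%).
- Cutoff 5 with extra placebo subjects: 68% at 36/18, 81% at 36/27, 85% at 66/24, 98% at 66/49.

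**The case against.** The best defence has three parts. First, nothing was miscalculated: Table 6 is right for Pearson, and the protocol powers and plans the same test. That stands; the fault is a mismatch inside the SAP between the test powered and the test planned.

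Second, the shortfall is narrow. The sentence fails only with an early stop, a placebo rate at the bottom of the grid, a treated rate near zero and few extra placebo subjects. The SAP expects 30 to 40% on placebo, and at 30% the SAP rule still gives 74%. The endpoint is secondary, and the sample size rests on the dose-finding simulation. This also stands, and it limits how much weight the point carries.

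Third, 36/12 leaves out placebo subjects whom the SAP plans to enrol, and with 18 to 27 on placebo the claim holds. That is true, but SAP 9.2 makes its claim for 36/12. The number of extras at an early stop is not fixed: they arise only when two cohorts await review, and their enrolment may be discontinued.

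A reader might infer that few extras are likely, because SAP 9.1 says of the lagged design that "this minor loss of efficiency is completely offset by the operational advantages of requiring fewer" extra placebo subjects. The documents do not support that step. The lag began only with protocol version 8.0, and if it needs fewer extras, the cohorts before it may have needed more.

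**Conclusion.** The point holds in a limited form. For 36/12 at 0.5% vs 20%, power under the SAP's own rule is about 44%, some 22 points below the figure in Table 6, at any expected-count cutoff above 0.50. Only a cutoff of 0.50 or lower, which keeps Pearson with an expected count of half a subject, restores 67.5%. At a 30% placebo rate the figure is about 74% instead of 82%. The 44% rests on no extra placebo subjects and a Day 30 scan for everyone; the number of extras decides whether >66% is true.

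A reader might go further and conclude that Table 6 is wrong, that the protocol contradicts itself, or that the bleed comparison is underpowered in general. None of these follows: the table matches Pearson, the protocol plans Pearson only, and both the full-run 84% and the >90% at a 40% placebo rate survive. It is a correction worth making to a secondary-endpoint power statement and shows no failure of the design.

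**What to change.** In the SAP only:

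1. State the expected-count cutoff in 8.2.
2. Recompute Table 6 by exact enumeration of that rule and name the test in the caption. Say that 36/12 and 66/22 exclude extra placebo subjects and assume complete Day 30 scans. Add rows with extras, for example 36/18, 36/27 and 66/49.
3. Replace the >66% sentence with: about 44% (20% placebo rate) or 74% (30%) at 36/12 without extra placebo subjects; at the 20% rate, higher with them (69% at 36/18, 76 to 88% at 36/27 depending on the cutoff); and about 84% at 66/22.
4. Only if the cutoff is 5, qualify >64% and >85% as about 56% at 36/12 and 83% at 66/22 without extra placebo subjects, and give the higher values with them from Step 6. If the cutoff is 1, both sentences can stand.

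The cost is one number in 8.2, a recomputed and labelled table, and one to three sentences in 9.2. Sample size, test and design stay as they are. The protocol needs at most a note that its figures are for Pearson without the fallback.
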